3.1.1 Screening Period (Day -7 to Day 1)

[figure not shown]
No study procedures will be performed prior to informing the patient about the study and obtaining written informed consent form (ICF). It is critical that patients receive study drug no more than 7 days from the onset of symptoms.

Screening evaluations will be completed prior to the randomization on Day 1. Outpatients with mild to moderate symptoms of SARS-CoV-2 infection not requiring supplemental oxygen therapy will be eligible for enrollment. Patients must have a local confirmation of SARS-CoV-2 infection by positive test result from a sponsor-supplied rapid SARS-CoV-2 diagnostic test or reverse transcription polymerase chain reaction (RT-PCR). If the patient has a RT-PCR result (sample collected within 72 hours prior to the study drug administration) confirming SARS-CoV-2 infection even if before signing the ICF, the patient can be enrolled without additional confirmation of SARS-CoV-2 infection at Screening.

If Screening visit date and the date of study drug administration (Day 1) are the same, all assessments scheduled for the Screening and Day 1 visit can be performed only once on the same day before randomization.

During the Screening Period, only one re-test for confirmation of SARS-CoV-2 infection will be allowed, if study drug can be administered no more than 7 days from onset of symptom based on the re-test result. The enrollment process is presented in [Figure 3-3](#).

Figure 3-3 Enrollment Process

Abbreviation: RT-PCR = reverse transcription polymerase chain reaction; SARS-CoV-2 = severe acute respiratory syndrome coronavirus 2.

1. Must be locally done by a sponsor-supplied rapid SARS-CoV-2 diagnostic test or RT-PCR. If the patient has a RT-PCR result (sample collected within 72 hours prior to the study drug administration) confirming SARS-CoV-2 infection even if before signing the ICF, the patient can be enrolled without additional confirmation of SARS-CoV-2 infection at Screening.
2. During the Screening Period, only one re-test for confirmation of SARS-CoV-2 infection will be

allowed, if study drug can be administered no more than 7 days from onset of symptom based on the re-test result.

3.1.2 Treatment Period (Day 1 to prior to End-of-Treatment Visit)

In the Treatment Period, the patients who meet all of the inclusion criteria and none of the exclusion criteria will be randomized on Day 1. If it is concluded that the patients are not eligible in Day 1 assessments before randomization, the patients will be considered as screening failure even if he/she was eligible based on assessments results performed during Screening Period.

In Part 1, approximately 300 patients will be randomly assigned in a 1:1:1 ratio (100 patients, respectively) to receive either a single dose of CT-P59 80 mg/kg, 40 mg/kg, or placebo on Day 1. In Part 2, approximately 1300 patients will be randomly assigned in a 1:1 ratio (650 patients, respectively) to receive either a single dose of CT-P59 40 mg/kg, or placebo on Day 1. All patients will be given optimal SoC (except potential antiviral drugs and/or possible anti-SARS-CoV-2 activity drugs).

Randomization will be stratified by age (≥ 60 years vs. < 60 years), baseline comorbidities (Yes vs. No, having at least one of cardiovascular disease, chronic respiratory disease, hypertension, diabetes mellitus, and pneumonia), region and participation in PK sub-study (Yes vs. No) in Part 1, and by age (≥ 60 years vs. < 60 years), baseline comorbidities (Yes vs. No, having at least one of cardiovascular disease, chronic respiratory disease, hypertension, diabetes mellitus, and pneumonia) and region in Part 2, respectively. In Part 1, a PK sub-study will be performed on the patients who signed informed consent to participate in a PK sub-study. Of the total number of 300 patients from Part 1, approximately 90 patients (30 patients per CT-P59 treatment groups and placebo group) will be included in the subgroup (PK) cohort, and PK samples from the patients in this cohort will be collected according to the schedule of assessments.

All enrolled patients in the study will complete the study visits during the treatment period either by visiting the study center, confinement in the study center, or home visiting services by health care professionals, whichever applicable according to the local regulation or at discretion of investigator.

Patients will comply with all appropriate visits and assessments. Patients will return to the study center at predefined time intervals for clinical assessments and blood sampling. At each visit, patients will be questioned about AEs and concomitant medications and will be monitored for the disease status. Patients will undergo the procedures at the time points specified in [Table 11-1](#), [Table 11-2](#), and [Table 11-3](#).

If a patient withdraws prematurely after the study drug administration, the patient will be asked to return to the study site on the next scheduled visit for the EOT assessments.

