The study will comprise of 3 study periods (including Screening, Treatment Period and Follow-up Period). An end-of-treatment (EOT) visit will occur on Day 90 and the total study duration is planned as 180 days for each patient. The overview of each part is presented in Figure 3-2.

Figure 3-2 Study Design Schema

Day	1	2	3	4	5	6	7	10	14	17	21	28	56	90	180
Administration of Study Drug	●														
Part 1 Viral Shedding (RT-qPCR and Cell culture)	●	●	●	●	●	●	●	●	●	●	●	●			
Part 2 Viral Shedding (RT-qPCR)	●		●				●	●	●		●	●			
Patient Diary							●								
SARS-CoV-2 infection related signs and symptoms assessment								●							
Pharmacokinetics (Part 1 only)	●	●	●		●		●	●	●			●	●	●	
Safety							●								

Abbreviations: SARS-CoV-2 = severe acute respiratory syndrome coronavirus 2; SoC = standard of care; RT-qPCR = reverse transcription quantitative polymerase chain reaction.

Notes: a) In Part 1, patients with body weight at or above 100 kg and who are allocated to CT-P59 80 mg/kg group or placebo group will receive 8,000 mg of CT-P59 or matching volume of placebo. In Part 2, patients with body weight at or above 200 kg will receive 8,000 mg of CT-P59 or matching volume of placebo. b) Of 1300 patients in Part 2, 822 high-risk patients will be included based on the sample size calculation (Section 7.5).

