3.1.3 Follow-Up Period (From End-of-Treatment Visit to Day 180)

For all patients including patients who withdraw prematurely after the study drug administration, each telephone call follow-up will occur biweekly from EOT visit up to Day 180. During the Follow-up Period, patients will be asked if they have any SARS-CoV-2 infection related signs and symptoms by telephone calls to capture the suspicious ADE occurrence.

4 Patient Selection and Withdrawal Criteria

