4.2 Withdrawal/Discontinuation of Patients from the Study

Patients are free to withdraw from the study at any time for any reason. The investigator may also withdraw the patients at any time in the interest of patient safety. The primary reason for withdrawal from the study must be recorded in the patient's medical record and in the electronic case report form (eCRF).

When possible, the sponsor should be notified of the withdrawal of a patient from the

study. For patients who early withdraw for any reason, all study procedures should be performed on the day of withdrawal (or the day after withdrawal) and all attempts should be made to complete all EOT assessments at planned time points of EOT visit. For patients who discontinued of Follow-up period, the reason of discontinuation will be recorded in the eCRF. Any comments (spontaneous or elicited) or complaints made by the patient, together with the reason for withdrawal from the study, and the date of cessation of study drug must be recorded in the eCRF and source documents. As it is vital to obtain follow-up data on any patient withdrawn because of an AE or serious AE (SAE) in every case, efforts must be made to undertake protocol-specified safety and follow-up procedures.

The reasons for withdrawal are as following:

- Withdrawal of consent
- Lost to follow-up
- Adverse event that would compromise his or her safety if he or she continues to participate in the study
- Death
- Investigator's decision

The status of patients who fail to complete final assessments will be documented in the eCRF. If necessary, the investigator may discuss with sponsor or its designee any patient's reason for withdrawal. The sponsor may be contacted if clarification is required on a case-by-case basis. All withdrawn patients will retain their patient number with the reason for withdrawal from the study.

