6.1.2 Disease Status Monitoring

Disease status including requirement of supplemental oxygen, intensive care unit transfer, mechanical ventilation use, hospitalization and rescue therapy due to SARS-CoV-2 infection will be monitored during the study period (from signing of ICF to EOT).

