6.2.1.2 Eliciting and Documenting Adverse Events

All AEs will be reported by the investigator via eCRF from the date patients signs the ICF until the last assessment date or EOT visit, regardless of the relationship to the study drug. Where an adverse drug reaction (ADR) (i.e., related to study drug) is ongoing at the EOT visit, the ADR will be followed up until one of the following: resolution or improvement from baseline, relationship reassessed as unrelated, confirmation from the investigator that no further improvement can be expected, end of collection of clinical or safety data, or final database closure.

At every study visit, patient will be asked a standard non-leading question to elicit any medically related changes in their well-being. They will also be asked if they have been hospitalized, had any accidents, used any new medications, or changed concomitant medication regimens (both prescription and over the counter medications).

In addition to patient's self-reporting of AEs ([Section 6.2.3](#)), AEs identified from any study data (e.g., laboratory values, physical examination findings, ECG changes) or identified from review of other documents that are relevant to patient safety will be documented on the AE page in the eCRF.

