10.1.1. Incidence of Treatment-Emergent Adverse Events

The TEAEs during Treatment Period will be summarized by treatment group, SOC, PT, relationship and intensity, displaying the number and percentage of patients with at least one TEAE using only the worst intensity recorded at each level of summarization. The

total number of events and number of patients with at least one TEAE over all SOC's will also be displayed. In addition, TEAEs regardless of relationship will be summarized.

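### After early withdrawal the documents give two timings for the EOT visit, and disease-status and routine AE collection end at EOT, so hospitalization and oxygen capture may stop before Day 28

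*Protocol*

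**What the plan says.** **When EOT occurs.** Protocol Section 3.1 fixes the planned visit: "An end-of-treatment (EOT) visit will occur on Day 90". For a patient who withdraws after dosing, Section 3.1.2 says that "the patient will be asked to return to the study site on the next scheduled visit for the EOT assessments". The Protocol synopsis, footnote 2 of Tables 11-1 and 11-2, SAP Section 4.1 and SAP Appendix 1 repeat this rule. Protocol Section 4.2 differs. It first asks that "all study procedures should be performed on the day of withdrawal (or the day after withdrawal"), and then that "all attempts should be made to complete all EOT assessments at planned time points of EOT visit".

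**What closes at EOT.**
- Disease status, including hospitalization, oxygen, ICU transfer and ventilation, "will be monitored during the study period (from signing of ICF to EOT") (Protocol Section 6.1.2).
- AEs are reported "from the date patients signs the ICF until the last assessment date or EOT visit, regardless of the relationship to the study drug" (Section 6.2.1.2). Section 6.2.1.3 gives consent to EOT as the window and, after EOT, provides only for serious adverse drug reactions.
- The heading of Section 3.1.2 ends the Treatment Period just before the EOT visit, and the SAP's main AE table is confined to it: "The TEAEs during Treatment Period will be summarized by treatment group, SOC, PT, relationship and intensity" (SAP Section 10.1.1). Section 10.1.3 does the same for serious events.

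**What continues.** Under Protocol Section 3.1.3, telephone contact goes on: "For all patients including patients who withdraw prematurely after the study drug administration, each telephone call follow-up will occur biweekly from EOT visit up to" the end of follow-up at Day 180. The specified content of the calls is SARS-CoV-2 signs and symptoms, to detect suspected antibody-dependent enhancement. SAP Section 10.1 states a longer AE window than the Protocol: to the end of the patient's participation.

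**The concern.** A single infusion cannot be undone by leaving the study, so a patient who withdraws in the first week is as exposed as one who completes. Under Section 3.1.2, that patient's EOT can fall within days of dosing and close two data streams with it.

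The first stream feeds the Part 2 primary endpoint. SAP Section 9.1 takes hospitalization and supplemental oxygen from the Disease Status Monitoring page. It identifies events by the presence of a record, and it gives no rule for a patient whose disease status was not collected to Day 28. Such a patient stays in the ITT Set – High Risk and would by default count as having no event.

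The second stream is safety. AE percentages use all patients in the treatment group as denominator, so a patient with a few days of routine AE collection counts the same as one with 90.

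**Working it through.** **Inputs.** Planned EOT is Day 90 (Protocol Section 3.1). Dosing is on Day 1. Scheduled visits after dosing are Days 2, 3, 5, 7, 10, 14, 17, 21, 28, 56 and 90 in Part 2 (Table 11-2). Part 1 adds Days 4 and 6 (Table 11-1). The primary endpoint runs to Day 28. Nominal days are used throughout and visit windows are ignored.

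**The plan's own figure.** Table 6-1 puts the Day 90/EOT sample 2,136 hours after the start of infusion. 2,136 / 24 = 89 days after dosing, which is Day 90.

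**The two timings compared.** Under Section 3.1.2, EOT is the first scheduled day after the withdrawal day. Days covered = EOT day − 1. Days lost = 90 − EOT day. Share of the primary window = (min(EOT day, 28) − 1) / 27. Under Section 4.2, EOT stays at Day 90 and, if the patient attends, nothing is lost.

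| Withdrawal day | EOT day (Section 3.1.2) | Post-dose days covered, of 89 | Days lost | Share of the 27 post-dose days to Day 28 |
|---|---|---|---|---|
| 2 | 3 | 2 | 87 | 7% |
| 4 | 5 | 4 | 85 | 15% |
| 8 | 10 | 9 | 80 | 33% |
| 15 | 17 | 16 | 73 | 59% |
| 22 | 28 | 27 | 62 | 100% |
| 29 | 56 | 55 | 34 | 100% |

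The results are the same in both parts. For the Day 4 withdrawal, 27 − 4 = 23 days of the primary window lie after EOT. From withdrawal on Day 21 onward the next visit is Day 28 or later, so the primary window is complete and only the AE window is shortened.

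**The calls.** After a Day 5 EOT, fortnightly calls fall on Days 19, 33, 47 and so on to Day 173. That is 12 calls, of which only Day 19 comes before Day 28.

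**Is there another route for a Day 12 hospitalization?** None is specified:
- Disease status has closed (Section 6.1.2).
- The medication records that SAP Section 9.1 also uses to qualify a hospitalization run only to EOT (Protocol Section 5.6).
- The SAE route does not replace them, because Section 6.2.1.3 excludes worsening of SARS-CoV-2 infection judged unrelated to study drug from AE and SAE reporting.
- The calls are specified for signs and symptoms only.

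A COVID-19 death does have a route, because SAP Section 9.1 also reads the End of Follow-Up page.

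**Power, as an illustration only.** The documents give neither a withdrawal rate nor a Part 2 dropout allowance. Assume that a fraction w in each arm withdraws and that all their events go unseen and count as non-events, which is the worst case for power under equal withdrawal. With p₁ = 0.071(1 − w), p₂ = 0.029(1 − w), p̄ their mean and n = 411 per arm, power = Φ{[(p₁ − p₂) − 1.96√(2p̄(1 − p̄)/n)] / √([p₁(1 − p₁) + p₂(1 − p₂)]/n)}.

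- w = 0: (0.042 − 1.96 × 0.01520) / 0.01513 = 0.806, so power is 79.0%, close to the stated 80%.
- w = 1%, 2%, 5%, 10%: power is 78.6%, 78.1%, 76.8%, 74.4%.

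**The case against.** The strongest reply is that the two EOT rules can coexist and that withdrawn patients are not abandoned. Section 4.2 does not itself name Day 90. It asks for best efforts, and a site could do an early visit and then a Day 90 visit. That is fair, so outright incompatibility is not shown. What stands is that no passage says which visit closes the data windows.

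Several stronger readings are tempting, but the documents do not support them.

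- *The patient is unobserved after Day 5.* Not so. Calls run to Day 180, and suspected antibody-dependent enhancement triggers the Table 11-3 assessments. Serious adverse drug reactions are reported after EOT, and adverse drug reactions ongoing at EOT are followed (Sections 6.2.1.2, 6.2.1.3 and 6.2.1.5). Reported SAEs are followed regardless of relationship (Section 6.2.1.4), and Section 4.2 requires efforts at safety follow-up when withdrawal was for an AE or SAE.
- *All AE collection stops at EOT.* The SAP says otherwise: its Section 10.1 window runs to the end of participation, and its listings flag Follow-Up Period events. This is a further mismatch with the Protocol. Events flagged that way still fall outside the Treatment Period tables.
- *Infusion-reaction rates are distorted.* Little affected: these events cluster around dosing, and scheduled hypersensitivity monitoring ends 4 hours after the start of infusion.
- *The SAP's Day 28 data rule for withdrawals is violated.* SAP Section 2 only says which existing data enter the report. It does not require collection.
- *The arms are biased against each other.* Possible if withdrawal differs by arm, but nothing in the documents shows that it does. The trial is double-blind and rescue therapy is allowed within the study. SAP Section 6 tabulates discontinuation reasons and time on study by arm, so an imbalance would be visible.

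It is also true that patients who refuse contact, are lost or have died cannot be recovered by rewording.

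**Conclusion.** The point holds for two data streams, disease status and the Protocol's routine AE collection, and on the condition that Section 3.1.2 governs. For a Day 4 withdrawal the two EOT timings differ by 85 days, and 23 of the 27 post-dose days to Day 28 have no specified capture route for hospitalization or oxygen. The gap in the primary endpoint arises only for withdrawals before Day 21.

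How many patients this touches cannot be stated. The withdrawal fractions in the power illustration are assumptions, and it overstates the loss for any patient whose event came before EOT. It is worth correcting before analysis because the primary endpoint depends on the affected page, SAP Section 9.1 has no rule for incomplete disease status, and the remedy is inexpensive.

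**What to change.** 1. Reconcile Protocol Sections 3.1.2 and 4.2, the synopsis, the schedule footnotes and the matching SAP text on when EOT occurs after withdrawal.
2. Reconcile the AE window in Protocol Sections 6.2.1.2 and 6.2.1.3 with SAP Section 10.1.
3. Define collection by study day, not by a movable visit, for every dosed patient who has not refused contact: at least Day 28 for the primary-endpoint components, with the medication records that qualify a hospitalization, and the planned Day 90 for AEs and SAEs.
4. At the fortnightly calls already scheduled for withdrawn patients, ask about hospitalization, oxygen and AEs since the last contact. After a Day 5 EOT, the calls near Days 19 and 33 would together cover the period to Day 28. For the last patients enrolled, the second answer must be in the database before the Day 28 lock.
5. Define the summary window in SAP Sections 10.1.1 and 10.1.3 by study day.

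The cost is wording changes and a few extra call questions. No new visit or procedure is needed. Reported AE rates may rise slightly.

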3.1.3 Follow-Up Period (From End-of-Treatment Visit to Day 180)

For all patients including patients who withdraw prematurely after the study drug administration, each telephone call follow-up will occur biweekly from EOT visit up to Day 180. During the Follow-up Period, patients will be asked if they have any SARS-CoV-2 infection related signs and symptoms by telephone calls to capture the suspicious ADE occurrence.

4 Patient Selection and Withdrawal Criteria

4.1 Selection of Study Population

It is expected that approximately 1600 patients will be enrolled at approximately 91 study centers in 16 countries in Part 1 and 106 study centers in 19 countries in Part 2. Male or female outpatients, aged 18 or above with SARS-CoV-2 infection (confirmed locally by a sponsor-supplied rapid SARS-CoV-2 diagnostic test or RT-PCR at Screening, or having a previous RT-PCR result [sample collected within 72 hours prior to the study drug administration] confirming SARS-CoV-2 infection even if before signing the ICF) will be considered for enrollment in the study if they meet all of the inclusion criteria and none of the exclusion criteria. ‘Outpatient’ in this study includes patients visiting the study center, and patients confined in the study center or quarantine at home due to local regulation or at discretion of the investigator.

4.1.1 Inclusion Criteria

Each patient must meet all of the following criteria to be randomized in this study.

1. Adult male or female patient, aged 18 or above.
2. Patient is diagnosed with SARS-CoV-2 infection at Screening by using the sponsor-supplied rapid SARS-CoV-2 diagnostic test or RT-PCR.

Note: If the patient had a RT-PCR result (sample collected within 72 hours prior to the study drug administration) confirming SARS-CoV-2 infection even if before signing the ICF, the patient can be enrolled without additional confirmation of SARS-CoV-2 infection at Screening.

Note: During the Screening Period, only one re-test for confirmation of SARS-CoV-2 infection will be allowed, if study drug can be administered no more than 7 days

from onset of symptom based on the re-test result.

3. Patient with conditions meeting all of the following criteria:
 - a. Oxygen saturation >94% on room air.
 - b. Not requiring supplemental oxygen.

***Note:** Patient with clinical signs of pneumonia but no signs of severe pneumonia (as defined in the [World Health Organization Guidance, 2020](#)) at the investigator's discretion is eligible for this study.*
4. Patient whose onset of symptom is no more than 7 days prior to the study drug administration. Onset time of symptom is defined as the time when the patient experienced the presence of at least one SARS-CoV-2 infection associated symptom.
5. Patient has one or more of the following (but not limited to) SARS-CoV-2 infection associated symptoms within but not more than 7 days prior to the study drug administration:
 - a. Feeling feverish
 - b. Cough
 - c. Shortness of breath or difficulty breathing
 - d. Sore throat
 - e. Body pain or muscle pain
 - f. Fatigue
 - g. Headache
 - h. Chills
 - i. Nasal obstruction or congestion
 - j. Loss of taste or smell
 - k. Nausea or vomiting
 - l. Diarrhea
6. Patient has one or more of the following SARS-CoV-2 infection associated symptoms present within 48 hours prior to the study drug administration:
 - a. Feeling feverish
 - b. Cough
 - c. Shortness of breath or difficulty breathing
 - d. Sore throat
 - e. Body pain or muscle pain
 - f. Fatigue
 - g. Headache

7. Patient (or legal guardian, if applicable) who is informed and given ample time and opportunity to read and/or understand the nature and purpose of this study including possible risks and side effects and must sign the ICF prior to participation in the study.

8. For both male and female patients, the patient and his or her partner of childbearing potential who agree to use a highly effective or medically acceptable methods of contraception during the course of the study and for 6 months following discontinuation of study drug as specified below:
 - Combined (estrogen and progestogen containing) or progestogen-only hormonal contraception associated with inhibition of ovulation
 - Intrauterine devices
 - True abstinence, when this is in line with the preferred and usual lifestyle of the patient. Periodic abstinence (e.g., calendar, ovulation, symptothermal, post-ovulation methods), declaration of abstinence of the duration of exposure to investigational drug, and withdrawal are not acceptable methods of contraception.
 - Condom in addition to use spermicide, hormonal contraceptive or barrier method in female; for male patient with his female partner of childbearing potential only. Spermicide condom (condoms coated with spermicide) use alone is not allowed.

Male and female patients and their partners who have been surgically sterilized for less than 6 months prior to the date of informed consent must agree to use any highly effective or medically acceptable methods of contraception. Menopausal females must have experienced their last period more than 12 months prior to the date of informed consent to be classified as not of childbearing potential.

